Appendix 2.2. Endpoint Derivations

Psoriasis Area Severity Index (PASI)

The Psoriasis Area and Severity Index quantifies the severity of a subject's psoriasis based on both lesion severity and the percentage of body surface area affected. Lesion severity: the basic characteristics of psoriatic lesions - erythema, induration and scaling - provide a means for assessing the severity of lesions. Assessment of these three main signs is performed separately for four areas of the body: head, upper limbs, trunk, and lower limbs. Average erythema, induration and scaling are rated for each body area according to a 5-point scale: 0, no involvement; 1, slight; 2, moderate; 3, marked; 4, very marked.

Body surface area (BSA) involvement: the extent (%) to which each of the four areas of the body is affected by psoriasis is assigned a numerical score according to the following area scoring criteria: 0, no involvement; 1, >0 to 9%; 2, 10 to 29%; 3, 30 to 49%; 4, 50 to 69%; 5, 70 to 89%; 6, 90 to 100%. For details see Table 5 of the protocol.

Derivation of PASI score

In each area, the sum of the severity rating scores for erythema, induration and scaling is multiplied by the score representing the percentage of this area involved by psoriasis, multiplied by a weighting factor (head 0.1; upper limbs 0.2; trunk 0.3; lower limbs 0.4). The sum of the numbers obtained for each of the four body areas is the PASI.

$$\text{PASI} = 0A_h(E_h + I_h + S_h) + 0.2A_u(E_u + I_u + S_u) + 0.3A_t(E_t + I_t + S_t) + 0.4A_l(E_l + I_l + S_l)$$

where A = area of involvement score; E = erythema; I = induration; S = scaling; h = head; u = upper limbs; t = trunk; l = lower limbs

The PASI score can vary in increments of 0.1 units from 0.0 to 72.0, with higher scores representing increasing severity of psoriasis.

PASI 50/75/90/100 response

At least 50/75/90/100% reduction in PASI relative to baseline PASI Score.

CCI [REDACTED]

[REDACTED]

[REDACTED]

[REDACTED]

CCI [REDACTED]

CC

CI

[Redacted]

CCI

[Redacted]

Physician Global Assessment (PGA)

The Physician Global Assessment of psoriasis is scored on a 5-point scale, reflecting a global consideration of the erythema, induration and scaling across all psoriatic lesions. Average erythema, induration and scaling are rated separately over the whole body according to a 5-point severity scale, scored from 0 to 4, with appropriate morphologic descriptors. The severity rating scores are summed and the average taken - the total average is rounded to the nearest whole number score to determine the PGA. The 5-point scale for PGA is: 0, "clear"; 1, "almost clear"; 2, "mild"; 3, "moderate"; 4 "severe".

CCI

[Redacted]

[Redacted]

[Redacted]

[Redacted]

CCI

[Redacted]

CCI [REDACTED]

[REDACTED]

[REDACTED]

[REDACTED]

Peak Pruritus Numerical Rating Scale (PP-NRS)

The intensity of pruritus will be assessed by a numerical rating scale (NRS), an 11-category numeric rating scale from 0 to 10. Pruritus will be evaluated by asking participants to assign a numerical score representing the worst imaginable itch over the last 24 hours on a scale from 0 to 10, with 0 indicating no symptoms and 10 indicating the worst imaginable symptoms. This item will be administered to all participants.

Select the number that best describes your worst itching due to psoriasis over the past 24 hours.
(Check one number only)

										
0	1	2	3	4	5	6	7	8	9	10
No itching									Worst possible itching	

CCI [REDACTED]

[REDACTED]

CCI [REDACTED]

CCI

CCI

Appendix 3. Statistical Methodology Details

Hochberg Testing Procedure

Consider testing null hypotheses H_{01}, \dots, H_{06} and let $p_i, i=1, \dots, 6$ denote the corresponding 1-sided p-values from the individual pairwise comparisons against the placebo arm prior to multiplicity adjustment. Furthermore, let $[1], \dots, [6]$ denote the order of the p-values so that $p[1] \leq p[2] \leq \dots \leq p[6]$. The procedure starts with the largest p-value $p[6]$ as follows:

1. If $p[6] < \alpha$ reject all null hypotheses, otherwise go to next step.
2. If $p[5] < \alpha/2$ reject hypotheses $H_{0[1]}$ through $H_{0[6]}$, otherwise go to next step.
3. If $p[k] < \alpha/(6-k+1)$, reject hypotheses $H_{0[1]}$ through $H_{0[k]}$.
4. If $p[1] < \alpha/6$, reject $H_{0[1]}$, otherwise stop and do not reject any hypotheses.

Alternatively, the unadjusted raw p-values can be read into Proc Multtest and adjusted using the HOC option in SAS's PROC MULTTEST.

```
data pvals;  
  Input Test$ Raw_P;  
Datalines;  
Test1 .xxxxx  
Test2 .xxxxx  
.....  
Test6 .xxxxx  
;  
Proc multtest pdata=pvals hoc out=new;  
run;
```

Appendix 4. SAS Code for Estimand 2 –Change from Baseline in PASI Score

```

libname C2501004 "/Volumes/app/..... /data_vai" ;

data adps;
set C2501004.adps;
if paramcd="PASI0246" and 2<avisitn<=9 and ANL01FL="Y" ;
keep subjid avisitn aval base trtan paramcd anl01fl;
run;

**example data for a single visit;
**created from systemic study ;
**ignore values, only used for illustration;

*Multiple Imputation;
**data already has one record per subject per visit even if;
**data is missing. Proc Mi needs missing values in order to impute;
data _data1;
set ADPS;
where avisitn=9;
run;

proc sort data=data1 out=data1 miss;
by trtan;
run;

*imputing aval=observed so range of endpoint 0-72 can be included in;
*mi procedure;
proc mi data=data1 _miss seed=2501004 nimpute=1000 out=outimp;
class trtan;
monotone regpmm(aval= base/details k=5);
mnar model( aval/modelobs = (trtan="1"));
var base aval;
run;
proc univariate data=outimp;
var aval;
histogram;
run;
data outimp1;
set outimp;
chg = aval - base;
**calculate chg from baseline;
pchg= ((AVAL - BASE)/BASE)*100;
**calculate pchg from baseline;
run;
proc sort data = outimp1 out = data1;

```

by imputation trtan usubjid;
run;

proc mixed data=data1 order=data;
 by imputation;
 class trtan;
 model CHG = trtan base;
 lsmeans trtan/ diff alpha=.1;
 ods output lsmeans=mmmr diff=dmrm(where=(trtan=1));
run;

**now use mianalyze on lsmean;
 **First sort by trtan;
proc sort data=mmrm out=lsout1;
 by trtan _imputation_;
run;
 **now mianalyze by trtan;
 **NB mianalyze only uses estimates and standard errors not CI limits etc.;

proc mianalyze data=lsout1 alpha=.1;
 **specify alpha for 90% CIs here;
 by trtan;
 modeleffects estimate;
 stderr stderr;
 ods output parameterestimates=lsmean;
run;

**now use mianalyze on lsmean differences;
 **First sort by trtan;
proc sort data=dmrm out=diffsout1;
 by trtan _imputation_;
run;
 **now mianalyze by trtan;
 **NB mianalyze only uses estimates and standard errors not CI limits etc.;

proc mianalyze data=diffsout1 alpha=.1;
 **specify alpha for 90% CIs here;
 by trtan;
 modeleffects estimate;
 stderr stderr;
 ods output parameterestimates=diff;
run;

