2.1.2. Secondary Estimand(s)

The secondary estimand will provide a population level estimate of the treatment effect of PF-06826647 on continuous endpoints, especially the change from baseline and the percent change from baseline in PASI scores under the hypothetical scenario that prohibited medication is not used regardless of dosing compliance.

- Population: *Participants with moderate to severe plaque psoriasis as defined by the inclusion and exclusion without the benefit of additional prohibited medications regardless of compliance.*
- Variable: Change from baseline or the percentage change from baseline in PASI at Week 16.
- Intercurrent Events: *A) Prohibited medication – all scores after participants receive prohibited medication will be omitted from the analysis and treated as missing scores. Missing scores will be imputed based on the assumption that participants do not benefit from the IP treatment. B) Withdrawal and all other events leading to missing data will be treated similarly as in A). C) Inadequate compliance – participants data will be used as recorded.*
- Population-level summary: The mean difference between treated and placebo arms of the change from baseline/percentage change from baseline PASI score.

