5.3. Methods to Manage Missing Data

The primary analysis will use the primary estimand binary endpoint set. This dataset by definition has no missing data since all missing values will have been set to a failure. Summaries will use the Observed Efficacy Set and will report results on an observed case (OC) basis. For continuous endpoint data, each landmark analysis (eg, Cross sectional analysis by week) missing data will be imputed using a control based imputation method. PROC MI will first be called at the visit and a control based method (implemented with the MNAR (Missing Not At Random)--option) will impute missing placebo observations under the assumption data are missing at random (MAR) and impute missing treatment observations assuming they are similar to corresponding placebo patients. Imputation will use the full conditional specification (FCS) method, the imputed data for the placebo arm will be combined for the analysis.

Summaries of continuous data will use the observed data only and no additional considerations are needed.

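### The main Week 16 PASI change analysis imputes missing placebo scores from baseline alone, so it is biased if dropout follows interim response; earlier PASI scores should be added

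*SAP*

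**What the plan says.** SAP 2.1.2 defines the secondary estimand E2 for change and percent change in PASI at Week 16. Scores after prohibited medication are dropped, and these and other missing scores follow one rule: "Missing scores will be imputed based on the assumption that participants do not benefit from the IP treatment". SAP 6.2.3.1 makes ANCOVA on the imputed data the main analysis.

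SAP 5.3 describes the imputation as a step at a single visit: "PROC MI will first be called at the visit". It will "impute missing placebo observations under the assumption data are missing at random (MAR") and treat missing active-arm scores as resembling placebo. It lists no predictors. It also says "Imputation will use the full conditional specification (FCS) method".

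Appendix 4 is therefore the only place where the predictors are given. The code:

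- first reads all post-baseline visits up to Week 16: "if paramcd='PASI0246' and 2<avisitn<=9 and ANL01FL='Y";
- then keeps one visit: "where avisitn=9";
- gives PROC MI only `base` and `aval`, and models the second on the first: "monotone regpmm(aval= base/details k=5";
- fits that model to one reference arm, taken here to be placebo: "mnar model( aval/modelobs = (trtan='1".

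The schedule in protocol 1.3 has PASI at Weeks 1, 2, 4, 6, 8, 12 and 16.

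**The concern.** With baseline as the only predictor, missing at random means that, given baseline, missingness has nothing to do with how the participant did after Day 1. That is much stronger than missing at random given the scores already seen.

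The plan makes a link with response plausible. Protocol 6.5 prohibits other psoriasis treatments, and E2 removes scores recorded after one is started. Participants who stop before Week 16 go to an Early Termination visit (protocol 4.1 and 7.1). A placebo participant who leaves because the disease is not improving is replaced by placebo completers who share only the baseline score. Those completers also supply the values for active-arm gaps, so an error in the placebo mean enters all four dose contrasts.

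Change and percent change in PASI are secondary endpoints, but this is their main analysis in a trial meant to inform dose selection.

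**Working it through.** **Share missing.** Protocol 9.2 plans 128 completers and 20% dropout: 128 / (1 − 0.20) = 160, as stated. In the placebo arm 32 / 0.8 = 40, so about 8 of 40 Week 16 scores could be missing.

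**Assumptions not in the documents.** Residual SD of PASI given baseline, 7 points; correlation ρ between interim (Week 12) and Week 16 residuals, 0.6 to 0.8; log-odds of dropout rising with the interim residual by 0.5 to 2 per SD.

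**Formulas.** Baseline-only imputation gives missing placebo participants the mean of the observed ones at the same baseline. So

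- placebo bias b = ρ × SD × m, where m is the mean standardised interim residual among those still observed;
- an active arm with loss d_a has that share filled from the same placebo model, so its mean shifts by d_a × b;
- contrast bias = d_a × b − b = −(1 − d_a) × b.

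**Results, 20% loss in both arms** (simulation, 400,000 per arm, regression means standing in for predictive mean matching):

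| Slope per SD | Placebo bias, ρ = 0.6 | Placebo bias, ρ = 0.8 | Contrast bias, ρ = 0.6 | Contrast bias, ρ = 0.8 |
|---|---|---|---|---|
| 0 | 0.0 | 0.0 | 0.0 | 0.0 |
| 0.5 | −0.40 | −0.54 | +0.33 | +0.43 |
| 1 | −0.73 | −0.98 | +0.59 | +0.78 |
| 2 | −1.10 | −1.47 | +0.89 | +1.17 |

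A negative placebo bias makes placebo look too good; a positive contrast bias moves the effect towards zero.

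The formulas reproduce the table. At slope 0.5, m = −0.404 / (0.6 × 7) = −0.096, and 0.8 × 7 × (−0.096) = −0.54. At slope 2, m = −1.103 / 4.2 = −0.263, and 5.6 × (−0.263) = −1.47; the contrast is 0.8 × 1.465 = 1.17. Taking ρ to 0.9 moves the steepest case to 6.3 × (−0.263) = −1.66, with contrast 0.8 × 1.66 = 1.3.

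**Other loss rates**, slopes 0.5 to 2. With 10% in both arms, placebo −0.2 to −0.8 and contrast +0.2 to +0.7. With 30% placebo and 10% active, placebo −0.6 to −2.1 and contrast +0.6 to +1.9.

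**With the interim score added**, large-sample placebo bias is within 0.01 points in every case. That is a best case, because simulated dropout depends on exactly the score that was added.

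**At trial size** (40 placebo, predictive mean matching with k = 5, about 20% loss, SD 7, correlation 0.8 to 0.9), placebo bias is about −0.4 to −1.3 points with baseline only and −0.1 to −0.3 with earlier PASI added. When dropout is unrelated to response there is no bias either way, but the SD of the imputation error falls from about 0.6 to 0.3–0.4 points.

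**Scale.** Protocol 2.2.3 gives a placebo-adjusted Week 4 change of −4.55 at 100 mg. A contrast bias of 0.3 to 1.2 is 7% to 26% of that (0.3 / 4.55 and 1.2 / 4.55).

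**The case against.** **The early scores are used elsewhere.** SAP 6.2.3.2 plans an MMRM for the same endpoint, and SAP 5.2.2 puts Weeks 1 to 16 in it. This stands as partial protection. But the MMRM is a sensitivity analysis and drops the control-based rule for active arms, so a difference from the main result could not be traced to one cause.

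**SAP 5.3 is not contradicted.** A reader might infer that the code breaks the missing-at-random commitment. The documents do not support that: 5.3 describes a single-visit imputation and names no predictors, so missing at random given baseline is a strong version of what it says, not a departure from it.

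**Fewer scores may be imputed than 20% suggests.** PASI is taken at Early Termination, about one week after the last dose, and the Week 16 window in Appendix 2.1 opens on Day 99. If Early Termination scores are windowed by day, someone stopping from about Day 92 (99 − 7) who attends may have an observed Week 16 score. SAP 4.5 also removes COVID-19 discontinuations. And if dropout follows the Week 4 score instead, with assumed correlations of 0.8 to 0.9, placebo bias falls to about 0.3–0.9 and contrast bias to 0.2–0.7. All of this stands and argues for the lower part of the range.

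**The bias is conservative and common to all doses.** This holds only if poor responders leave and active-arm loss is equal. The inherited share, 1 − d_a, differs by dose when dropout does.

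**The code is only an example.** Its comments say to ignore the values. It nevertheless carries the study's library, endpoint code and seed, and the version history records its revision.

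**Conclusion.** The point holds as a conditional one, and the change is worth making. The main E2 analysis is unbiased for the placebo mean only if missingness, given baseline, is unrelated to later PASI. If poor responders leave, then at 20% loss and under the assumed SD, correlation and slopes, the placebo mean is about 0.4 to 1.5 points too low and each contrast about 0.3 to 1.2 points too close to zero. If good responders leave, the sign reverses. Only the range should be reported.

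Three stronger readings go too far. One is that bias is certain: nothing in the documents shows that dropout will follow response. Another is that adding earlier visits removes the bias: with about 32 placebo completers as donors it shrinks but does not vanish. The third is that the primary result is at risk: SAP 4.4 and 6.1.1.1 set missing PASI 90 responses to failure, so this model is not used there. The mismatch between FCS in SAP 5.3 and MONOTONE in Appendix 4 is a documentation error with little numerical effect while only one variable is incomplete.

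**What to change.** 1. Impute placebo gaps at Week 16 from baseline plus a short list of earlier PASI scores, for example Weeks 8 and 12 or the last available visits, in visit order. Keep the list short: a trial-size check with all of Weeks 1 to 12 as predictors left 0.2 to 0.6 points of placebo bias, because donors resembling poor responders are scarce.
2. State how intermittent missed visits are filled first, since a monotone method needs a monotone pattern.
3. Within each completed data set, impute active-arm gaps from the completed placebo data given baseline only, so the E2 no-benefit rule is unchanged.
4. List the predictors in SAP 5.3, and make 5.3 and Appendix 4 name the same method. Once earlier visits enter, the choice matters more than it does now.

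No new data are needed. The cost is some extra programming, a few sentences in the SAP, and a few more parameters fitted to about 32 placebo completers. The gain is less placebo bias if dropout follows response, and better precision even if it does not.

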5.2.2. Analyses for Continuous Endpoints

Landmark (cross-sectional) analysis of key continuous endpoints will use analysis of covariance (ANCOVA). The ANCOVA model will include terms for treatment arm and baseline score of the dependent variable. Least-squares means at the mean overall baseline score will be presented along with 90% confidence intervals.

Mixed model repeated measures (MMRM) models will be used. The fixed effects of treatment, visit (Weeks 1, 2, 4, 6, 8, 12 and 16), and treatment-by-visit interaction will be included. Visit will be modeled as a categorical covariate. Unstructured covariance matrix will be assumed for the model errors. Compound symmetry covariance matrix will be used if the model with unstructured covariance doesn't converge.

When modeling the change from baseline values, the variable for visit will start with the first post-baseline visit, and the actual baseline value will be included as a covariate. At each visit, estimates of least square mean (LSM) values and the LSM differences between the PF-06826647 treated groups and placebo group will be derived from the model. The corresponding p-values and 90% confidence intervals will also be derived from the model.

Unless stated otherwise, descriptive summary statistics for all continuous variables will be presented on mITT Observed Efficacy Set by treatment group and will include the following: n, mean, median, standard deviation, minimum and maximum.

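### The SAP Appendix 4 code for the E2 analysis of PASI change, as printed, pools the four dose contrasts into one estimate, and no reading of the listing yields one dose-minus-placebo result per dose

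*SAP*

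**What the plan says.** The prose of the SAP is clear. The opening of Section 6 asks for a pairwise comparison of each active group with placebo, with a point estimate, 90% confidence interval and p-value. Section 5.2.2, in its paragraph on change-from-baseline models, says that "the LSM differences between the PF-06826647 treated groups and placebo group will be derived from the model". Section 2.1.2 defines the E2 summary as the mean difference between treated and placebo arms. Section 6.2.3.1 makes ANCOVA with control-based imputation the main analysis of PASI change and percent change at Week 16.

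Appendix 4 gives the program:

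- The imputation step uses "seed=2501004 nimpute=1000 out=outimp", and its MNAR statement names treatment level 1 as the group from which missing values are modelled. Section 5.3 says the method will "impute missing treatment observations assuming they are similar to corresponding placebo patients", so level 1 is placebo.
- The imputed data are sorted "by imputation trtan usubjid" and analysed with "proc mixed data=data1 order=data".
- All pairwise LS-mean differences are requested, with no control level named.
- The differences are filtered by "ods output lsmeans=mmmr diff=dmrm(where=(trtan=1", sorted by `trtan` and `_imputation_`, and combined by "proc mianalyze data=diffsout1 alpha=.1" with `BY trtan`.

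**The concern.** After the filter, `trtan` equals 1 in every row. The four doses can then be told apart only by `_trtan`, which the printed code never uses. A `BY` statement on a constant separates nothing, so the combining step would average across doses and count the dose response as imputation variance.

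At stake is the main analysis of PASI change in a trial meant to support dose selection. A constant `BY` variable produces no error message. A programmer who noticed one output row where four were expected would have to repair the code outside the pre-specified listing.

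**Working it through.** The documents report no E2 result, so there is no figure to reproduce. The check has two parts.

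**1. Tracing the listing**

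- Placebo is level 1 (MNAR statement with Section 5.3). Ascending sort plus data order makes it the first level in PROC MIXED.
- A difference row is `trtan` minus `_trtan`, with the earlier level in `trtan`. Rows with `trtan=1` are therefore placebo minus each dose.
- There are five arms (SAP Section 2.2), so four such rows per imputation: 4 × 1000 = 4000 rows in one `BY` group.

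Underscores are visibly damaged in this block: `by imputation;` lacks them, and a data set appears as both `_data1` and `data1`. The possible readings are:

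| Filter | Sort and `BY` key | Result |
|---|---|---|
| `trtan=1` (as printed) | `trtan` (as printed) | one pooled estimate, placebo minus dose |
| `trtan=1` | `_trtan` | four estimates, placebo minus dose |
| `_trtan=1` | either | no rows under the printed ascending sort |

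None gives four dose-minus-placebo estimates. For the second row to be the true text, the underscore must have been lost in both the sort and the MIANALYZE `BY` statement, while `_imputation_` survived on that same sort line.

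**2. Size of the effect if the printed form is authentic**

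The steps were emulated in Python: predictive mean matching from placebo (k = 5, 1000 imputations), ANCOVA of change on arm and baseline, then Rubin's rules with T = W + (1 + 1/M)B. SAS was not run, and intervals use 1.645 × SE.

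*From the documents:* arm sizes 40/20/20/40/40 and 20% dropout, used as missingness (SAP Section 2.2); Week 4 effects of −4.55 for 100 mg and −14.02 for 400 mg (Protocol Section 2.2.3).

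*Assumed:* effects of −2 for 50 mg and −9 for 200 mg; baseline PASI mean 20, SD 6; residual SD 5, 7 or 9.

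One simulated trial at SD 7, placebo minus dose:

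| Dose | Estimate | SE |
|---|---|---|
| 50 mg | 4.64 | 1.94 |
| 100 mg | 8.84 | 1.91 |
| 200 mg | 8.92 | 1.59 |
| 400 mg | 12.58 | 1.61 |

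- Merged estimate: (4.64 + 8.84 + 8.92 + 12.58)/4 = 34.98/4 = 8.75.
- Merged variance: W = 2.81, B = 8.25, M = 4000. √(2.81 + 1.00025 × 8.25) ≈ 3.33 from these rounded inputs; 3.32 unrounded. The 90% interval is 3.28 to 14.21.
- Source of B: the squared deviations of the four estimates from their mean sum to about 31.6, and 31.6/4 = 7.9. So 7.9 of the 8.25 is spread between doses, not imputation noise.

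All scenarios:

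| Scenario | Merged SE | Per-dose SE | Ratio |
|---|---|---|---|
| SD 5 | 3.39 | 1.26–1.54 | 2.2–2.7 |
| SD 7 | 3.32 | 1.59–1.94 | 1.7–2.1 |
| SD 9 | 3.34 | 1.93–2.34 | 1.4–1.7 |
| SD 7, second seed, 50 mg at −1 | 4.24 | 1.99–2.51 | 1.7–2.1 |
| Equal effects of −8, SD 7, run 1 | 1.95 | 1.57–1.91 | 1.0–1.2 |
| Equal effects of −8, SD 7, run 2 | 2.52 | 1.65–2.06 | 1.2–1.5 |

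In the second-seed run the merged interval was −1.10 to 12.85, although 100, 200 and 400 mg each excluded zero when combined separately. In the other three dose-response runs the merged interval excluded zero.

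**The case against.** The strongest objection is that the merging turns on one character in a block whose underscores are plainly damaged. The code comments that also say `trtan` repeat those of the LS-means step, where that key is right, so they are weak evidence. This stands: the merging cannot be confirmed from the extracted text.

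A reader might infer that the trial will report a single PASI effect with an inflated error and a reversed sign. The documents do not support that, for three reasons:

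- The governing prose asks for per-dose results.
- The listing as printed would not run to completion. Besides the data set naming above, `subjid` is kept but `usubjid` is sorted on, and LS means are written to `mmmr` but read from `mmrm`. Some of these faults may themselves come from extraction.
- One output row in place of four would probably be noticed.

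The sign is also largely a matter of convention. Sections 2.1.2 and 5.2.2 name treated before placebo but do not state the subtraction order, and reversing it leaves the standard error, interval width and p-value unchanged.

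Nor is this the only dose-specific evidence. The PASI 90 and PASI 75 comparisons and the supplementary MMRM of PASI change do not use this code. Protocol Section 9.4.1 applies no multiplicity adjustment to the continuous secondary endpoints.

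The objection does not rescue the listing. Restoring underscores gives either contrasts in the opposite direction or an empty data set.

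**Conclusion.** Wrong as written. The printed differences step pools four placebo-minus-dose contrasts as 4000 imputations of one parameter, contrary to SAP Section 6. Whether the source listing does the same must be checked. If it reads `BY _trtan`, only the direction remains to be corrected.

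The scope is the main E2 analysis of PASI change, a secondary endpoint. The primary PASI 90 analysis is untouched. The loss of dose-specific estimates follows from the printed code alone, given standard SAS behaviour. The inflation of the standard error is illustrative and depends on how far the dose effects differ: about 1.4- to 2.7-fold in the dose-response scenarios, and 1.0- to 1.5-fold in the two equal-effect runs. It rests on assumed residual SDs, baseline distribution, and 50 mg and 200 mg effects.

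**What to change.** Check Appendix 4 against the source listing. Whatever it shows, replace the differences request with `LSMEANS trtan / DIFF=CONTROL('1')` and remove the `where` filter. `TRTAN` then holds the dose, the estimate is dose minus placebo, and the printed `BY trtan` and its comments become correct.

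In the same edit, use one name each for the LS-means data set, the imputation input data set, the subject identifier and the imputation index. Repeat the PROC MIXED and MIANALYZE steps for `PCHG`, which the code derives but does not model although Section 6.2.3.1 plans percent change. It would also help to state the subtraction order in Section 2.1.2.

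The cost is a few lines in an SAP appendix, with no effect on data collection, sample size or the primary analysis.
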